Recently, magnetic resonance imaging (MRI) has become one of the most common and reliable diagnostic methods in medicine. The results of the still improving imaging performances, new functionalities, and more affordable prices represent a pronounced trend toward equipping hospitals and clinics with MRI scanners [1]. The rapid development of this technology has created the need to construct devices capable of monitoring vital signs of at-risk patients during MRI examinations. The risk group in the context of MRI includes neonatal, paediatric, disabled, anesthetised, and insensible patients [2]. The monitoring of life functions is also recommended for persons with implanted pacemakers, patients developing reactions to contrast media, and persons with mental disorders who may not be able to communicate with the system operator or to use the alarm button. However, efforts are being made to monitor at least some basic physiological parameters such as respiration and heart activity [3] during each MRI examination, regardless of the patient category.

Although MRI is a noninvasive method of investigation and does not expose patients to ionizing radiation, it has some psychological effects on patients. Some researchers [4],[5] have already demonstrated that 5 to 10% of patients undergoing MRI examinations experience severe claustrophobia or panic attacks during the scanning process, whereas 30% report milder distress and fear. Such increased stress stimuli and arousal may in turn lead to a phenomenon known as hyperventilation, which is increased ventilation of the lungs and significant acceleration and deepening of the breath, often resulting in fainting.

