The acquisition of physiological signals relies on placing the sensor mat under the patient's back during standard MRI procedures. Before and after the MRI scanning, the patient gets to complete the State Trait Anxiety Inventory (STAI) questionnaire. The part of the body that is being scanned and the time of the MRI examination are not relevant. Although an average MRI scanning lasts from 20 to 40 minutes, we assume that the study will be no longer than 1 hour as the administration of contrast media may prolong the survey. Up to 200 MRI patients of different age, weight and sex will be involved in the study. Exclusion criteria from the study are the same as exclusion criteria from MRI procedures. The sensor mat does not cause health changes in patients and the study is of observational type. The analysis will concern changes in RR and/or HR during MRI, with particular emphasis on the beginning and the end of the examination, i.e., 1- or 2-minute parts of the whole recording, as it shown in Fig. 1. The mean RR and/or HR values recorded at the beginning and the end of the MRI scanning will be referred to the STAI X-1 scores gathered before and after the MRI scanning, respectively. The research scheme includes also the collection of the STAI X-2 subscale before the MRI scanning.

[figure not shown]

Fig. 1. General scheme of the study.

Methodology

Fibre-optic sensor system

The sensor system consists of a sensor mat, an interrogation module and a laptop personal computer (PC). As shown in Fig. 2, the sensor mat includes a spring-board that converts body movements including lung- and heart-induced motions into strain, and a single fibre Bragg grating (FBG) or an FBG matrix bonded to the board measures this strain. The instantaneous spectral position of the FBG reflection peak can be calibrated in terms of the respiration and heart activity readings. Thus, the sensor also acquires ballistocardiographic (BCG) signals, and to operate effectively, the mat has to be placed between the back of the patient (as close to the heart as possible) and the mattress of the MRI track table.

[figure not shown]

Fig. 2. Sensor mat based on a (a) single FBG and (b) FBG matrix.

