MIAM is both a research institute and medical centre, where data management and information security are provided in accordance with the ISO IEC 27001 standard. A copy of the certificate is included as **Appendix A**.

Statistical Analysis Plan

Descriptive statistic methods will be used to evaluate the state anxiety and RR and/or HR indicators, as well as to assess the difference between the first and second anxiety measurement. A correlation analysis with the Pearson product-moment correlation coefficient will be performed to check if the initial RR and/or HR level is related to state anxiety measured right before the MRI study.

Since we hypothesise about the individual variability of the change in the RR and/or HR levels during an MRI session, a growth mixture model analysis [22] will be performed to statistically differentiate the subject groups according to the trends in repeated measures of RR and/or HR. After that, the analysis will be performed with the use of the Student's t-test to check whether the so-identified groups differ on the magnitude of change in the state anxiety observed during the study. An Alpha level of 0.05 will be used in all of the statistical tests.

The analysis will be performed using R statistical software version 3.4.0 [23]. The Growth mixture model analysis will be performed using the lcmm package version 1.7.7 [24]. The power analysis will be performed with the pwr package version 1.2-1 [25]. Plots will be created using the ggplot2 package version 2.2.1 [26].

Quality Assurance

MIAM has a quality management certificate based on the ISO 9001:2008 and AQAP 2120:2009 requirements. Copies of the certificates are included as **Appendix B**.

Expected Outcomes of the Study

Correlations between the STAI X-1 scores collected before and after the MRI scanning and the mean RR values recorded at the beginning and the end of the MRI scanning, respectively, are expected. Similarly, correlations between the STAI X-1 scores and the HR indicators should also be noticeable. We also expect the STAI X-2 scores will be useful in estimating the risk of anxiety symptoms during MRI.

At least two manuscripts, one containing the results of the STAI scores in relation to RR, and the other containing the results of the STAI and HR analysis, will be submitted for publication.

Dissemination of Results and Publication Policy

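### The plan neither records nor analyses factors that may alter heart or respiration rate independently of anxiety (pacing, rate-controlling drugs, a sedative or anxiolytic before the scan)

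*Combined protocol and SAP*

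**What the plan says.** Study Design defines eligibility by reference: "Exclusion criteria from the study are the same as exclusion criteria from MRI procedures". It does not list those exclusions. The sample is a ceiling: "Up to 200 MRI patients of different age, weight and sex will be involved in the study".

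The Statistical Analysis Plan uses RR and HR, pooled over all patients, in two ways:

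- A Pearson correlation, with no covariates, to "check if the initial RR and/or HR level is related to state anxiety measured right before the MRI study".
- A growth mixture model to "statistically differentiate the subject groups according to the trends in repeated measures of RR and/or HR", followed by a t-test comparing the resulting groups on change in state anxiety.

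The Project summary adds a third use: deriving RR/HR values that may point to a dangerous degree of anxiety.

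The test level is fixed ("An Alpha level of 0.05 will be used in all of the statistical tests"). For power only the software is named ("The power analysis will be performed with the pwr package version 1.2-1"), with no effect size, SD or target power.

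The background section says "The monitoring of life functions is also recommended for persons with implanted pacemakers" and "The risk group in the context of MRI includes neonatal, paediatric, disabled, anesthetised, and insensible patients". These sentences describe MRI patients in general, not this study's enrolment.

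The STAI section requires the state scale just before and just after scanning. The Ethics section requires signed consent immediately beforehand.

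**The concern.** MRI exclusions are adopted here without any link to whether a patient's heart or respiration rate can respond to anxiety. A patient on a rate-controlling drug, or one who took an anxiolytic before arriving, may show a rate that says less about anxiety than another patient's would. For HR, the same may be true of a paced patient.

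If such patients are pooled unmarked, three outputs are exposed. The correlation may be diluted or otherwise shifted. The trend classes may partly separate treated from untreated patients, so the t-test would compare something other than anxiety-related trajectories. The anxiety-indicating values may be set from a mixture of two populations.

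Anxiety detection is the stated main purpose and the third objective. If these factors are not recorded at the visit, they may be hard to recover later.

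**Working it through.** **Plan's own figure.** There is none to reproduce, because no power calculation is reported. Everything below is illustrative.

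**Inputs.** From the documents: n = 200 (the ceiling) and alpha 0.05. Assumed: a two-sided test; true correlation r = 0.20 or 0.30; affected share f = 10-20%; affected patients' rates unrelated to their anxiety, with the same SD as other patients unless stated.

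**Formulas.** Power (Fisher z) ≈ Φ(atanh(r)·√(n−3) − 1.960); the opposite tail is negligible at the larger correlations. If affected patients' mean HR differs by d SD and their mean STAI by e SD, the pooled correlation is

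[(1−f)r + f(1−f)de] / √{[1+f(1−f)d²][1+f(1−f)e²]},

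which reduces to r(1−f) when d = e = 0.

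**Reference.** For r = 0.20: atanh(0.20) = 0.2027; × √197 = 14.04 gives 2.846; minus 1.960 is 0.886; power 81%. For r = 0.30, power is 99%. The smallest correlation detectable with 80% power at n = 200 is about 0.197.

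**Affected at random (e = 0).** Example: r = 0.20, f = 0.20, d = −0.8 gives 0.16/√(1 + 0.16 × 0.64) = 0.16/1.050 = 0.152.

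| True r | f | Pooled r, d = 0 (power) | Pooled r, d = −0.8 (power) | Affected excluded: n (power) |
|---|---|---|---|---|
| 0.20 | 10% | 0.18 (72%) | 0.175 (70%) | 180 (77%) |
| 0.20 | 20% | 0.16 (62%) | 0.152 (58%) | 160 (72%) |
| 0.30 | 10% | 0.27 (97%) | 0.263 (97%) | 180 (98%) |
| 0.30 | 20% | 0.24 (93%) | 0.229 (90%) | 160 (97%) |

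**Affected patients differ in both HR and STAI (f = 20%).**

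- HR −0.5 SD, STAI +0.5 SD, r = 0.20: (0.16 − 0.04)/1.04 = 0.115, power 37%. For r = 0.30: (0.24 − 0.04)/1.04 = 0.192, power 78%.
- HR −0.5 SD, STAI −0.5 SD, r = 0.20: (0.16 + 0.04)/1.04 = 0.192, almost unchanged.
- HR −1 SD, STAI −0.5 SD, r = 0.20: (0.16 + 0.08)/√(1.16 × 1.04) = 0.219, slightly higher.

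**Use rising with anxiety.** Simulation with 2 million draws; log-odds of use rise by 1 per SD of anxiety (odds × 2.7); 13-24% affected overall; r = 0.30.

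- With rates 0.8 SD lower, pooled r is about 0.16-0.08. The range covers an affected-patient SD of 0.5 to 1. Power falls from 99% to about 63-21%.
- With the same selection but no lowering of the rate, pooled r is about 0.25-0.21.
- Excluding affected patients gives r about 0.29-0.28 and power about 97-94%, but removes about 39-59% of the most anxious tenth of patients.

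**The case against.** Several stronger readings are tempting, and the documents do not support them.

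- *Paced patients enter the study.* A reader might infer this from the background section. That section describes MRI patients generally, and the MRI exclusion list is not given, so their entry is unconfirmed. The plan only fails to bar them by a criterion of its own.
- *Anaesthetised or insensible patients enter the correlation.* Consent just before the study and two STAI completions around the scan remove them in practice. Light sedation and oral drugs remain possible.
- *Affected signals cannot reflect anxiety.* This is physiological reasoning from outside the documents, and only *may not* is defensible. It is weaker for RR, which pacing and rate-controlling drugs need not change.
- *The correlation is biased towards zero or reversed.* The direction depends on who is treated. A drug that lowers both state anxiety and HR leaves the correlation about the same or slightly higher. The steep fall at r = 0.30 needs two unsupported assumptions together: anxiety-related use and a 0.8 SD lower rate.
- *The sensor concept could be wrongly judged a failure.* Feasibility, signal quality and RR/HR detection (the first two objectives) do not depend on the link with anxiety.
- *The restricted set should be primary.* The plan labels no analysis primary, and it aims at routine MRI use, so the all-comer correlation is a legitimate target. Restriction could also drop many of the most anxious patients, who matter most for the third objective.

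All of these limits stand. They do not supply the missing record: the plan as available would not show who is treated, and so could not show which pattern applies.

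**Conclusion.** The concern holds in a limited form. Eligibility rests on unlisted MRI exclusions, and no available part of the protocol records or handles pacing, rate-controlling drugs, or a pre-scan sedative or anxiolytic. The unadjusted correlation, the RR/HR classes and the anxiety-indicating values may therefore be distorted by an amount and in a direction that the study could not determine.

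The effect could be negligible or material. Random use in 10-20% of patients matters little if the true correlation is 0.30, and moderately if it is 0.20, which is close to the limit of what 200 patients can detect. Only anxiety-related use combined with lowered rates does serious damage. All of this rests on assumed shares, shifts and correlations. Some pages, including the consent forms, were not available for review.

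This is an inexpensive improvement in data collection and analysis, not a flaw that invalidates the design.

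**What to change.** Keep enrolment and the all-comer analysis as planned, and add:

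1. Three yes/no items recorded at consent: pacemaker; rate-controlling drug; sedative or anxiolytic taken before the scan.
2. In the Statistical Analysis Plan, a pre-specified restricted or adjusted sensitivity analysis reported beside the all-comer correlation. If restricted, the HR analysis uses patients with none of the three, and the RR analysis uses patients without a sedative or anxiolytic.
3. A cross-tabulation of the growth mixture classes against the three items, shown with the t-test result.

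The cost is three data items and a few sentences in the plan. The restricted set will be smaller and may under-represent the most anxious patients, so it should be read alongside the all-comer result and not in place of it.

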The fibre-optic sensor system consists of a sensor mat, an interrogator and a personal computer (PC), and records respiratory and BCG signals in patients during MRI. The metal-free sensor mat is placed under the patient's back, does not pose a threat to the patient and has no influence over the quality of imaging. The interrogation module detects the optical signal including vital signs, and the PC with software developed for signal processing and visualisation enable the MRI operator to monitor patient's RR and HR.

Up to 200 MRI patients in different age, weight and gender groups will be participated in the study. They will be asked to complete the State Trait Anxiety Inventory (STAI) questionnaire in order to estimate anxiety level before and after the MRI scanning. Relations between the STAI X-1 scores and the mean RR and/or HR values recorded at the beginning and the end of the MRI scanning will be analysed using descriptive statistic methods. Finally, the values of the physiological parameters, which may indicate a dangerous level of anxiety will be determined. Positive results of the clinical evaluation will predestine the fibre-optic sensor system to be implemented in routine MRI procedures.

General information

Protocol Title

Clinical evaluation of a fibre-optic sensor system for monitoring respiration activity and heart work during MRI examinations

Short title

Evaluation of an MRI-compatible vital signs sensor system

Acronym

OPTO-MRI

Sponsor

Military Institute of Aviation Medicine (MIAM)
[name]
[name]
Poland

Primary Investigator (PI)

[name], D.Sc., Ph. D.
[name]
[name]
Poland
[contact]
email: [contact]

Other medical and/or technical institutions involved in the research

No other co-operators

Rationale & background information

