Hyperventilation has numerous theoretical and empirical links to anxiety, panic, and fear episodes [6],[7]. This phenomenon was investigated in order to understand psychological and physiological mechanisms connected with hyperventilation that cause and maintain anxiety. On the other hand, attempts were also made to find a link between hyperventilation and the therapies used to treat different types of anxiety disorders. Some results [8] support the idea of higher variability and irregularity in the respiratory patterns of subjects with panic disorder. Other clinical studies [9] have shown that controlling and normalising the subject's breathing activity helps to reduce both anxiety and panic symptoms. On the basis of this assumption, different training and therapeutic programs [10] have been created and carried out with the aim of teaching patients to breathe in a specific way to avoid or reverse hyperventilation, e.g., capnometry-assisted respiratory training (CART) [11]. Furthermore, attempts have also been made to study the relationship between different anxiety disorders and cardiological parameters. The literature [12] reveals an increased heart rate (HR) level in a group of people suffering from panic, anxiety disorders, and hyperventilation symptoms.

In light of recent scientific reports, it seems obvious that MRI examinations can be a source of extreme stress and cause anxiety and panic symptoms in some patients. People who experience anxiety, fear, or hyperventilation during an MRI scan may either discontinue the procedure altogether or refuse to undergo MRI surveys in the future. In practice, it is very important to identify those who are likely to panic and experience anxiety-related symptoms in the MRI unit as early as possible, because only early detection ensures that appropriate actions can be taken to avoid psychological discomfort for the patient undergoing the scan and unnecessary use of the machine, as well as staff involvement in the entire procedure. Real-time monitoring of certain life functions in the patient, such as respiration rate (RR) and HR, can be helpful in controlling the arousal and anxiety level associated with the MRI examination itself and predicting the probability of a panic attack.

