Conventional monitoring equipment is not designed to work in the harsh MRI environment, distinguished by a magnetic induction of 1.5 T, 3.0 T, or even higher values and with radio frequency (RF) impulses of considerable electromagnetic (EM) field intensity [13]. The presence of metal or electronic components under such conditions can cause burns on the patient's skin and alter the EM field distribution and, thus, degrade the quality of imaging. Additionally, the signal transmitted using electrical conductive wires is vulnerable to the effects of a strong EM field, which complements the list of drawbacks of typical electronic measuring devices. On the other hand, optical sensors are fully penetrable in terms of the EM radiation applied in MRI, causing no interference. They are free from metal parts and function via optical fibres, resulting in their immunity to EM fields.

Study goals and objectives

The main objectives include:

1. Testing the sensor system with participation of MRI patients, where the result measures relate both to feasibility and health outcomes.
2. Verifying the signal quality, detecting RR and HR, and checking long-term measurement capabilities of the sensor system.
3. Analysing changes in RR and HR in the context of the system ability to detect a high level of stress, hyperventilation and other symptoms of claustrophobia in MRI patients.

Study Design

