A schematic of the research setup is shown in Fig. 3. The sensor mat is placed in the MRI chamber underneath the chest area of the patient to ensure proximity to the heart and lungs. A few meters optical fibre is threaded through a wall opening and connected via a fibre-optic for angled physical contact (FC/APC) -type connector to an FBG interrogation module in the operation room. To interrogate the sensor mat, a commercially available DL-BP1-1501A broadband light source by *DenseLight Semiconductors* [14] with I-MON 256/512 USB monitor by *Ibsen Photonics A/S* [15], or sm130-700 integrated unit by *Micron Optics* [16] will be used. The data from the interrogation module is sent via an USB or Ethernet interface

to the laptop PC with software developed for signal visualisation, data archiving as well as automatic determination of RR and HR.

[figure not shown]

Fig. 3. Research setup.

MRI scanner

Achieva 1.5T by *Philips* [17] or Discovery MR750w 3.0T by *General Electric* [18] MRI scanners will be used in the study.

STAI

In order to measure anxiety in patients undergoing MRI procedures, the Polish version of the STAI by Spielberger et al. [19] was used. The inventory is designed to measure the level of anxiety as a current state in response to a given situation (the X-1 subscale) as well as a relatively stable personal trait (the X-2 subscale). Evaluation of anxiety level in patients will be conducted according to a repeated measurement protocol. The subjects will complete the STAI X-1 subscale twice, i.e., just before entering the MRI scanner and immediately after leaving the scanner. The STAI X-2 subscale will be completed before the MRI scanning. As a result, the level of experienced anxiety before and after the MRI scanning, as well as the level of anxiety as a constant personality trait in patients, will be obtained.

Safety Considerations

The presence of the sensor mat during the MRI examination does not pose a threat to the patient. Because the sensor mat is free from metal elements, it is fully penetrable by the EM radiation used in MRI and causes no interference. We have previously showed that the fibre-optic sensor is transparent to the MRI system and does not introduce any artefacts into the spin echo (SE) T1 weighted and T2 weighted or to the gradient echo (GE) T2 weighted imaging sequences [20],[21].

Follow-Up

No recommendations other than for standard MRI procedures.

Data Management

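### Objective 3 asks whether RR and HR reveal anxiety provoked by the scan, but no anxiety rating refers to the time inside the scanner

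*Combined protocol and SAP*

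**What the plan says.** **The aim.** Objective 3 (Study goals and objectives) is "Analysing changes in RR and HR in the context of the system ability to detect a high level of stress, hyperventilation" and claustrophobia symptoms in MRI patients. The Rationale wants real-time RR and HR to help in "controlling the arousal and anxiety level associated with the MRI examination itself and predicting the probability of a panic attack". The Project summary traces the stress to the confined space, isolation and noise of the scanner, and promises that "the values of the physiological parameters, which may indicate a dangerous level of anxiety will be determined".

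**The anxiety measure.** Methodology, STAI describes X-1 as a rating of anxiety as a current state, made in response to a situation. On timing it says: "The subjects will complete the STAI X-1 subscale twice, i.e., just before entering the MRI scanner and immediately after leaving the scanner". The same section states the yield as anxiety before and after scanning, plus trait anxiety from X-2, which is completed before the scan.

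**The RR/HR measure.** Study Design analyses changes during MRI, "with particular emphasis on the beginning and the end of the examination, i.e., 1- or 2-minute parts of the whole recording".

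**The analyses.** Start-window means are paired with pre-scan X-1, and end-window means with post-scan X-1 (Study Design; Expected Outcomes). The Statistical Analysis Plan names a Pearson correlation for the start pairing. It also fits a growth mixture model to RR and/or HR over the session, followed by a t-test to "check whether the so-identified groups differ on the magnitude of change in the state anxiety observed during the study". For the trait scale, Expected Outcomes says: "We also expect the STAI X-2 scores will be useful in estimating the risk of anxiety symptoms during MRI".

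**The concern.** The sensor records throughout the scan, but the anxiety it is meant to reveal is rated only outside the scanner. A patient may become very anxious part-way through, settle, and leave with much the same X-1 score as at entry. If the planned analyses then show little relation, the sponsor could not tell whether RR and HR fail to track anxiety or whether anxiety was rated at the wrong moments. A positive result would also say less than it appears to. It would show a link with anxiety before or after the scan, while the values meant to flag dangerous anxiety would have no rating of in-scan anxiety behind them.

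**Working it through.** The plan gives no figure to reproduce on this point. The check is which anxiety measure each analysis uses and what time it refers to.

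**Step 1: where the target anxiety lies.** Objective 3 does not itself say that the anxiety arises during the scan. That reading comes from the Project summary (scanner conditions as the cause), the Rationale (real-time monitoring of the examination) and Study Design (RR and HR recorded during MRI).

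**Step 2: the named RR/HR-anxiety analyses.**

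| Analysis | RR/HR input | Anxiety input | Refers to time in the scanner? |
|---|---|---|---|
| Start pairing | mean of start window | X-1 before entry | No |
| End pairing | mean of end window | X-1 after exit | No |
| Mixture groups, t-test | trajectory over the session | X-1 after minus X-1 before | No |

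Three of three use X-1 alone, and neither of the two X-1 ratings refers to time in the scanner. The change tested in the third row is the difference between the two X-1 scores, because no other state measure is collected. X-2 is a trait scale with no named analysis against RR or HR, and the text gives no measure of anxiety during the scan to test it against. Problems Anticipated mentions patients' anxiety reactions only as something to be handled, not as a recorded outcome.

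**Step 3: what this can hide.** Let A(t) be anxiety at time t. Ratings of the moment give A(entry) and A(exit), and their difference is A(exit) - A(entry). The highest A(t) in between enters neither. Two patients with equal entry and exit states but different peaks have the same X-1 pair. How often this happens depends on the timing and length of episodes and on carry-over into the exit rating. None of these is given, so no attenuation or patient count can be computed.

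**Step 4: choice of RR/HR summary for an added item.** Write each 2-minute epoch mean as resting level plus deviation. The absolute peak is then resting level + highest deviation, so differences in resting RR and HR enter it directly. Peak minus start window is highest deviation - start deviation, and the resting level cancels. In an illustrative simulation (10 to 20 epochs, one anxiety-driven episode), the rank correlation adjusted for number of epochs behaved as follows:

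| Resting SD, in epoch SDs | Absolute peak |
|---|---|
| 0 | 0.40 |
| 1 | 0.28 |
| 2 | 0.18 |
| 4 | 0.10 |

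Peak minus start window stayed near 0.28. The levels depend on the assumed settings. The pattern follows from the algebra.

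**Step 5: why to adjust for number of epochs.** Scans of 20, 40 and 60 minutes give 10, 20 and 30 two-minute epochs. The expected maximum of that many independent standard-normal values is 1.539, 1.867 and 2.043. By chance alone the peak rises by 1.867 - 1.539 = 0.33 epoch SD from 20 to 40 minutes, and by 2.043 - 1.539 = 0.50 from 20 to 60. With lag-1 autocorrelation of 0.6 (assumed) the rises are 0.38 and 0.59.

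**Step 6: precision of the added analysis.** Fisher z with SE = sqrt((1 + r²/2)/(n - 3 - k)), k = 1 covariate and r = 0.30 assumed, so z = 0.3095:

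- n = 200: SE = sqrt(1.045/196) = 0.0730; z limits 0.3095 ± 1.96 × 0.0730; 95% CI 0.165 to 0.424.
- n = 100 (an assumed lower case, since 200 is a ceiling): SE = sqrt(1.045/96) = 0.1043; 95% CI 0.105 to 0.473.

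Adjusting for the start-window value as a second covariate changes 196 to 195 and leaves the interval practically the same.

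**The case against.** The strongest defence is that the design is coherent for what it pairs. Each X-1 rating is matched with the RR/HR window nearest in time. X-1 is a reaction to a situation, and the second rating follows the scan at once, so some scan anxiety probably carries over. This stands in part. It makes the loss uncertain, but it does not make the exit score a rating of time in the scanner, and the STAI section itself describes the yield as before and after.

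A second defence is that hyperventilation is a change in breathing, which RR can partly show without any rating. This stands, although no criterion is given. A reader might infer that objective 3 as a whole cannot be met; the documents do not support that.

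A reader might also infer that the middle of the recording is thrown away. The text does not say so. Study Design stresses the two ends without excluding the rest, the mixture model works on repeated measures over the session, and Fig. 1 is not available here. The gap lies in the anxiety reference, not in how much of the recording is used.

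Finally, the proposed item is also asked outside the scanner and exchanges a timing gap for recall error on one question. That is a genuine limit, but the item at least asks about the right period.

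**Conclusion.** The point holds for the stress and anxiety part of objective 3, for the values meant to flag dangerous anxiety, and for the expectation placed on X-2. Every named RR/HR-anxiety analysis, three of three, depends on ratings that describe the patient outside the scanner. As planned, the study can relate RR and HR to anxiety before and after the scan. It cannot show whether they reflect anxiety felt in the scanner.

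This assumes that objective 3 means scan-provoked anxiety, as the summary and rationale indicate, and that X-1 is answered for the moment of completion. The size of the effect is unknown. Objectives 1 and 2, hyperventilation read from RR, and the start-window pairing that serves early identification stand as they are. The change is worth making because it is cheap and the missing rating cannot be recovered later; it is not a reason to reject the design.

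**What to change.** Keep all planned analyses and add the following:

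1. One item beside the post-scan X-1: highest anxiety felt during the scan, 0-10.
2. For each patient, the highest 2-minute mean RR and HR over the recording, expressed relative to the start window (as a change, or adjusted for the start-window value). Relate each to the item by rank correlation adjusted for number of epochs, with a 95% CI.
3. The number of epochs lost to movement artefact, and a sensitivity analysis that keeps them, because movement may itself accompany distress.
4. The relation of X-2 to the same item.
5. A statement that any values offered as signs of dangerous anxiety are exploratory.

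The cost is one question at a point where a questionnaire is already given, plus analysis time on data handled by "software developed for signal visualisation, data archiving as well as automatic determination of RR and HR". The item should be in place before recruitment or early in it. Its limits should be stated: a retrospective single rating with recall error and no exact timing, which supports an association and does not validate a threshold. A patient already anxious at the start may show little change from the start window, which is one reason to keep the start pairing.

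If the item is not added, the alternative costs only wording: restrict objective 3's anxiety conclusion and the proposed danger values to state anxiety before and after the scan.
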